### 13.1.1.7 Laboratory

Nominal Visit	Target Day	Window Definition (Study Day)
Baseline	1	Last evaluation prior to or on Study Day 1 before dosing
Month 1	31	Study Day 2 to 61
Month 3	92	Study Day 62 to 137
Month 6	183	Study Day 138 to 229
Month 9	275	Study Day 230 to 320
Month 12	366	Study Day 321 to End of Double-blind Period Date
Month 18	548	End of Double-blind Period Date +1 to 685
Month 24	731	Study Day 686 to End of Open-label M24 Study Period Date
Month 30	913	End of Open-label M24 Study Period Date +1 to Study Day 1004
Month 36	1096	Study Day 1005 to 1187
Month 42	1278	Study Day 1188 to 1369
Month 48	1461	Study Day 1370 to 1552
Month 54	1643	Study Day 1553 to 1734
Month 60	1826	Study Day 1735 to 1917

Data are collected every 6 months after Month 36 until the end of the study. To be processed and sent to the central laboratory during the primary analysis period; to be analyzed at local laboratories following the primary analysis period.

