### 7.3.16 Month 24 ( $\pm$ 14 Days) / Early Termination for Month 12 to Month 24 of the Primary Analysis Period

#### For all subjects

- PRO/ClinRO questionnaires: OPAQ SV, EQ-5D-5L, LAD, and BPI worst pain (should preferably be completed before any other study procedures are performed)
- Physical examination
- Vital signs: blood pressure, temperature, and pulse
- Height and weight
- Blood sample for serum chemistry, hematology, and anti-romosozumab antibody
- Lateral spine x-rays (lumbar and thoracic), submitted to the central imaging vendor as soon as possible following the visit
- DXA scans of lumbar spine and proximal femur, submitted to the central imaging vendor as soon as possible following the visit
- Nonvertebral and suspected clinical vertebral fracture reporting
- Adverse event and concomitant medications data collection
- ALN dispensation (open-label, 6-month supply)
- Unused ALN collection (open-label)

For subjects participating in the Imaging and PK/BTM/Biomarker sub-study

- Fasting blood sample for P1NP and sCTX
- Blood sample for sclerostin and iPTH
- Blood sample (serum and plasma) for novel biomarker development
- For subjects participating in the imaging components: QCT of the spine, submitted to the central imaging vendor as soon as possible following the visit

Note: If a subject terminates early from the study between the Month 12 and Month 24 visits, Month 24 procedures except ALN dispensation are to be completed at that time. DXA scans and lateral spine x-rays should be performed if at least 6 weeks have elapsed since the previous one.

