### 13. Appendices

#### 13.1 Technical Detail and Supplemental Information Regarding Statistical Procedures and Programs

##### 13.1.1 Visit Windows

Per protocol, all monthly study visits up to Month 13 have a  $\pm 7$ -day window. Following the 12-month double-blind ALN-controlled study period, study visits have a  $\pm 14$ -day window. To allow for variations in scheduling, the following sets of visit windows will be used to assign evaluations to a most appropriate nominal visit for analysis. Furthermore, there will be no gaps between visit windows in order to include as many data points as possible for summarization.

Regardless of the width of the visit window, if more than 1 visit falls within the defined window, the result from the visit closest to the target day will be used. If 2 evaluations are of the same distance from the target day, the result from the later visit will be used. If more than one evaluation on the same date and time, the average of the results will be used. Only laboratory results collected from the central laboratory will be averaged in the case of duplicate results. Results not included for analysis will be included in listings only.

For LOCF imputation, the last evaluation on or prior to the upper bound of the specified window (ie, no lower bound) would be used for each nominal visit.

The window for the monthly phone contact in between clinic visits throughout the study is  $\pm 7$  days. The window for the end of primary analysis period phone call is  $-14$  days to end of primary analysis. Unscheduled follow-up clinic visits after the monthly phone contact have a  $+ 21$ -day window. The window for the end of study phone contact is  $-14$  days to  $+ 7$  days.

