### 13.1.1.3 DXA (lumbar spine and proximal femur) for imaging component of Sub-study

Nominal Visit	Target Day	Window Definition (Study Day)
Baseline a	1	Last evaluation prior to or on Study Day 1
Month 6	183	Study Day 2 to 274
Month 12	366	Study Day 275 to End of Double-blind Period Date + 30
Month 18	548	End of Double-blind Period Date +31 to Study Day 639
Month 24	731	Study Day 640 to End of Open-label M24 Study Period Date +30
Month 36	1096	≥ Study Day End of Open-label M24 Study Period Date +31

a If results from baseline DXA are not available, the results from scan taken on or before Study Day 14 will be considered baseline values and not the Month 6 values.

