### 13.1.1.8 Antibody (AB)

Nominal Visit	Target Day	Window Definition (Study Day)
Baseline	1	Last evaluation prior to or on Study Day 1
Month 1 a	31	Study Day 2 to 61
Month 3	92	Study Day 62 to 137
Month 6	183	Study Day 138 to 274
Month 12	366	Study Day 275 to End of Double-blind Period Study Day
Month 18	548	End of Double-blind Period Date +1 to 685
Month 24	731	≥ Study Day 686

a Any antibody assessment done on Study Day 1 but after the administration of the investigational product will be classified into Month 1.

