**13.1.1.9 Weight and Height**

Nominal Visit	Target Day	Window Definition (Study Day)
Baseline	1	Last evaluation prior to or on Study Day 1
Month 6	183	Study Day 2 to 274
Month 12	366	Study Day 275 to End of Double-blind Period Date
Month 18	548	End of Double-blind Period Date +1 to Study Day 639
Month 24	731	Study Day 640 to End of Open-label M24 Study Period Date
Month 30	913	End of Open-label M24 Study Period Date +1 to Study Day 1004
Month 36	1096	Study Day 1005 to 1187
Month 42	1278	Study Day 1188 to 1369
Month 48	1461	Study Day 1370 to 1552
Month 54	1643	Study Day 1553 to 1734
Month 60	1826	Study Day 1735 to 1917

Data are collected every 6 months after Month 36 until the end of the study.

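### The laboratory and antibody visit windows split Month 18 from Month 24 at day 685/686, while the five other SAP tables that split these visits use 639/640, so some exit blood samples take the label of the more distant visit

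*SAP*

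**What the plan says.** SAP 13.1.1 sets analysis windows so that each evaluation goes to the visit it best fits. When a window holds more than one evaluation, "the result from the visit closest to the target day will be used"; results not used appear only in listings.

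For Months 18 and 24 (targets day 548 and day 731), the tables differ:

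- **Laboratory (13.1.1.7):** Month 18 runs to day 685, and Month 24 is "Study Day 686 to End of Open-label M24 Study Period Date".
- **Antibody (13.1.1.8):** Month 18 is "End of Double-blind Period Date +1 to 685", and Month 24 is "≥ Study Day 686".
- **Weight and height (13.1.1.9):** Month 18 is "End of Double-blind Period Date +1 to Study Day 639", and Month 24 is "Study Day 640 to End of Open-label M24 Study Period Date". The bone-marker (13.1.1.6), PRO/ClinRO (13.1.1.10) and vital-sign (13.1.1.12) tables make the same cut.
- **Sub-study DXA (13.1.1.3):** Month 24 is "Study Day 640 to End of Open-label M24 Study Period Date +30", again a cut at 639/640.

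Protocol 7.3.16 creates blood samples in the disputed interval: "If a subject terminates early from the study between the Month 12 and Month 24 visits, Month 24 procedures" (all except ALN dispensation) are done at exit. Those procedures include chemistry, hematology and anti-romosozumab antibody, as well as vital signs, height, weight and the PRO questionnaires. SAP 10.6.9 applies no imputation to the laboratory tabulations.

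**The concern.** Two of the seven tables that separate Month 18 from Month 24 use a later cut than the rest, and the SAP does not say why. For a woman who leaves on days 640 to 685 this has three effects.

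- Her exit chemistry, hematology and antibody results are labelled Month 18, although she is nearer Month 24.
- If she also has a sample nearer day 548, the closest-to-target rule keeps that one. Her exit result then leaves the by-visit summaries and she contributes nothing at Month 24. If she has no such sample, the exit result stays in the summaries, under Month 18.
- One visit is split across two labels. At an exit visit on day 660, blood is Month 18 while vital signs, weight and PRO scores are Month 24.

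At stake is how completely and how consistently the last on-study blood results of withdrawing women appear in the by-visit safety tables.

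**Working it through.** **1. Where the midpoint falls.** (548 + 731) / 2 = 639.5, which gives a cut at 639/640. That reproduces the five other tables. The laboratory and antibody cut is 685 − 639 = 46 days later.

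**2. Whether these two tables use midpoints elsewhere.** They do at their other fixed-day cuts.

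- Laboratory: (31 + 92)/2 = 61.5, stated 61/62; (92 + 183)/2 = 137.5, stated 137/138; (183 + 275)/2 = 229, stated 229/230; (275 + 366)/2 = 320.5, stated 320/321; (913 + 1096)/2 = 1004.5, stated 1004/1005. The later six-monthly cuts follow the same pattern.
- Antibody: (183 + 366)/2 = 274.5, stated 274/275.
- Only Month 18/24 departs. A cut at 685/686 would be the midpoint of day 640 and day 731, (640 + 731)/2 = 685.5, as if there were a Month 21 visit at day 640. That is only a guess at the origin: neither these tables nor the protocol's visit schedule has a Month 21 clinic visit.

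**3. Distance of the affected days from each target.**

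| Study day | From Month 18 (548) | From Month 24 (731) |
|---|---|---|
| 640 | 92 | 91 |
| 662 | 114 | 69 |
| 685 | 137 | 46 |

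All 46 days from 640 to 685 are nearer Month 24.

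**4. Which sample survives.** An on-schedule Month 18 visit (±14 days) falls on days 534 to 562, at most 14 days from target. An exit sample on days 640 to 685 is at least 92 days from that target, so the Month 18 sample always wins. An on-schedule Month 24 visit falls on days 717 to 745, outside the disputed interval.

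**5. How many women.** Inputs are 4,000 randomized, with dropout of 10% in year 1 and 8% per year after (SAP 3.2.1).

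- On study at day 640: 4,000 × 0.90 × 0.92^(274/365) ≈ 3,382.
- Leaving over the next 46 days: 3,382 × (1 − 0.92^(46/365)) ≈ 35, about 1% of those on study.
- Sensitivity to the rate, treating q as a constant yearly hazard: 3,600 × [exp(−q × 274/365.25) − exp(−q × 320/365.25)] gives about 18 at q = 0.04, 34 at q = 0.08 and 49 at q = 0.12.
- Antibody: only samples from women exposed to romosozumab are analysed (Protocol 7.8.4). With 1:1 allocation, 35 / 2 ≈ 18.

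These figures count every leaver. Protocol 8.1 lists death, loss to follow-up and full withdrawal of consent among the reasons for removal, and many such women give no exit sample.

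**The case against.** The case on the other side is mostly about consequence, and much of it stands.

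**Exit data are not lost to the safety analysis.** A reader might infer that withdrawing women's last results disappear from the safety evaluation. The documents do not support that. SAP 10.6.9 attaches the windows to the by-visit statistics and figures. The worst-value shifts, worst calcium and Hy's law review are not expressly windowed, and the same section says the incidence rates take in all open-label laboratory measurements for women who took open-label ALN. Grade 3 and 4 values are listed. SAP 10.6.11 counts antibody positivity at any visit as well as at each visit, and judges persistence from the last time point tested. On that wording these outputs keep the exit sample.

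**Removal from the summaries is conditional.** It needs a competing sample nearer day 548. That is the usual case for a woman who attended Month 18, but it is not universal.

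**No stated midpoint rule is broken.** The SAP sets an aim of best fit, not a nearest-target rule, and departs from nearest-target at period boundaries in the same laboratory table. Month 12 closes no later than day 396, so a sample on day 400 becomes Month 18 although it is 34 days from Month 12 and 148 from Month 18. Month 24 closes by day 761, so day 770 becomes Month 30 at 143 days against 39. Those boundaries follow defined period dates. The 685/686 cut follows none, so what remains is an unexplained inconsistency between tables.

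**The numerical effect is small.** About 1% of women at most is negligible for a by-visit mean, and the windows are the same in both arms.

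**Conclusion.** The inconsistency is real and can be checked from the SAP alone. As written, the laboratory and antibody tables label samples on days 640 to 685 as Month 18 although each is nearer Month 24. Where a nearer Month 18 sample exists, the exit sample goes to listings only.

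The size is at most about 35 women, or about 18 for antibody, if the SAP's dropout rates hold. The number would be lower in practice, because it assumes that every leaver attends an exit visit and, for removal from the summaries, that she already has a Month 18 sample. The effect is confined to by-visit laboratory and antibody summaries. No efficacy endpoint uses either table. This is a minor correction that is worth making because it is cheap and stops one visit from carrying two labels.

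**What to change.** In SAP 13.1.1.7 and 13.1.1.8, end Month 18 at Study Day 639 and start Month 24 at Study Day 640, leaving the other bounds as they are. If 685/686 is intended, state the reason instead.

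The cost is two numbers in each of two tables. No on-schedule visit moves: Month 18 visits on days 534 to 562 and Month 24 visits on days 717 to 745 keep their labels. The one trade-off is that some exit samples taken up to 91 days before the Month 24 target enter the Month 24 summary. The five other tables already accept this.

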### 13.1.1.8 Antibody (AB)

Nominal Visit	Target Day	Window Definition (Study Day)
Baseline	1	Last evaluation prior to or on Study Day 1
Month 1 a	31	Study Day 2 to 61
Month 3	92	Study Day 62 to 137
Month 6	183	Study Day 138 to 274
Month 12	366	Study Day 275 to End of Double-blind Period Study Day
Month 18	548	End of Double-blind Period Date +1 to 685
Month 24	731	≥ Study Day 686

a Any antibody assessment done on Study Day 1 but after the administration of the investigational product will be classified into Month 1.

**13.1.1.9 Weight and Height**

Nominal Visit	Target Day	Window Definition (Study Day)
Baseline	1	Last evaluation prior to or on Study Day 1
Month 6	183	Study Day 2 to 274
Month 12	366	Study Day 275 to End of Double-blind Period Date
Month 18	548	End of Double-blind Period Date +1 to Study Day 639
Month 24	731	Study Day 640 to End of Open-label M24 Study Period Date
Month 30	913	End of Open-label M24 Study Period Date +1 to Study Day 1004
Month 36	1096	Study Day 1005 to 1187
Month 42	1278	Study Day 1188 to 1369
Month 48	1461	Study Day 1370 to 1552
Month 54	1643	Study Day 1553 to 1734
Month 60	1826	Study Day 1735 to 1917

Data are collected every 6 months after Month 36 until the end of the study.

**13.1.1.10 OPAQ-SV, LAD, BPI and EQ-5D**

Nominal Visit	Target Day	Window Definition (Study Day)
Baseline	1	Last evaluation prior to or on Study Day 1
Month 6	183	Study Day 2 to 274
Month 12	366	Study Day 275 to End of Double-blind Period Date
Month 18	548	End of Double-blind Period Date +1 to Study Day 639
Month 24	731	Study Day 640 to End of Open-label M24 Study Period Date
Month 30	913	End of Open-label M24 Study Period Date +1 to Study Day 1004
Month 36	1096	Study Day 1005 to 1187
Month 42	1278	Study Day 1188 to 1369
Month 48	1461	Study Day 1370 to 1552
Month 54	1643	Study Day 1553 to 1734
Month 60	1826	Study Day 1735 to 1917

Data are collected every 6 months after Month 36 until the end of the primary analysis period.

### 13.1.1.11 Post-fracture OPAQ-SV and EQ-5D-5L, LAD and BPI

Visit Relative to Fracture	Target Day	Post-fracture Visit Window Definition
Pre-fracture Baseline	NA	Last evaluation prior to the reported nonvertebral or clinical fracture date
Month 1 *	31	The scheduled monthly post-fracture visit within day 16 to day 45 post-fracture window
Month 2 *	61	The scheduled monthly post-fracture visit within day 46 to day 75 post-fracture window
Month 3 *	91	The scheduled monthly post-fracture visit within day 76 to day 105 post-fracture window

\*If more than one actual visit falls within the same defined window, the closest visit to the target day will be considered for analysis. If two assessment actual dates are at the same distance from the target day, the later visit will be considered for analysis.

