### **7.12 Patient Reported and Clinician Reported Outcomes**

PRO and ClinRO assessments are to be completed before any other study procedures are performed. All subjects will complete the OPAQ SV, EQ-5D-5L, LAD, and BPI worst pain questionnaires every 6 months during the primary analysis period (refer to the Schedule of Assessments, [Appendix A](#)). Subjects who have reported a nonvertebral or a suspected clinical vertebral fracture during the 12-month double-blind ALN-controlled study period (ie, up to the Month 12 study visit) will start postfracture PRO/ClinRO assessments. These subjects will be asked to complete the OPAQ SV, EQ-5D-5L, LAD, and BPI worst pain questionnaires. Postfracture PRO/ClinRO assessments will be performed at the visit during which the nonvertebral fracture or suspected clinical

vertebral fracture has been reported and at the 3 consecutive monthly study visits. Subsequent nonvertebral or suspected clinical vertebral fractures will trigger a new cycle of postfracture PRO/ClinRO assessments. Postfracture PRO/ClinRO assessments will only be performed up to the Month 12 study visit; data collection is not required beyond Month 12 even if the fracture has been reported at the Month 10, Month 11, or Month 12 study visits.

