##### **Pre-fracture Baseline for PRO/ClinRO Endpoints**

Pre-fracture baseline for PRO/ClinRO endpoints is the closest recorded PRO/ClinRO measurements before the visit of reporting a nonvertebral fracture or clinical vertebral fracture.

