##### **PRO/ClinRO Endpoints at Report of Fracture**

PRO/ClinRO Endpoints at Report of Fracture is the first recorded PRO/ClinRO measurements within 45 days after the date of the reported non-vertebral fracture or clinical vertebral fracture.

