#### **BPI Worst Pain Score**

The analyses of changes from study baseline at months 6, 12, 18, 24, 30, and 36 in BPI worst pain score will be performed using the repeated measures model as described in [Section 10.5.1.6](#). The analyses of changes from pre-fracture baseline at month 1, 2 and 3 after reporting a clinical fracture in BPI worst pain score will be performed using the repeated measures model adjusting for age strata, presence or absence of severe

vertebral fracture at baseline, treatment, visit, fracture type, pre-fracture baseline score, change from pre-fracture baseline at report of fracture and treatment by visit interaction. The missing BPI worst pain score at reporting of the fracture will be handled by multiple imputation.

The proportion of subjects with a clinically meaningful improvement in worst pain in 3 months after experiencing a nonvertebral or clinical vertebral fracture (defined as a 2-point improvement in the BPI worst pain scale compared with the fracture reporting visit) will be analyzed using a logistic regression model adjusting for age strata, presence or absence of severe vertebral fracture at baseline, treatment, fracture type, worst pain score at report of fracture and change from pre-fracture baseline at report of fracture. The proportion of subjects with a clinically meaningful improvement in worst pain at each post fracture reporting visit and within 3 months from pre-fracture baseline will be analyzed using same approach.

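### The post-fracture Month 1 window lies wholly inside the at-report window, so one questionnaire can serve as both, and the day-0 anchor is inconsistent

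*SAP*

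**What the plan says.** **At-report value.** SAP 6.1.1 uses "the first recorded PRO/ClinRO measurements within 45 days after the date of the reported non-vertebral fracture", with parallel wording for clinical vertebral fractures.

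**Months 1 to 3.** SAP 13.1.1.11, in a table whose visits are labelled relative to fracture, sets Month 1 as "The scheduled monthly post-fracture visit within day 16 to day 45 post-fracture window", Month 2 as "The scheduled monthly post-fracture visit within day 46 to day 75 post-fracture window" and Month 3 as "The scheduled monthly post-fracture visit within day 76 to day 105 post-fracture window". The targets are days 31, 61 and 91. If several visits share a window, the one closest to target is used, and the later one if they tie.

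**Collection.** Protocol 7.12 has the questionnaires completed at the visit where the fracture "has been reported and at the 3 consecutive monthly study visits", up to Month 12. Those visits carry a window of ±7 days (Protocol 7.1.2).

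**Use.** SAP 10.5.4 defines the pain responder by a "2-point improvement in the BPI worst pain scale compared with the fracture reporting visit". Its post-fracture repeated measures models for OPAQ-SV, EQ-5D-5L VAS, BPI and LAD include the change from pre-fracture baseline at report of fracture as a covariate.

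**Pre-fracture baseline.** SAP 6.1.1 uses "the closest recorded PRO/ClinRO measurements before the visit of reporting a nonvertebral fracture", and Protocol 10.5.2.1 likewise works back from the reporting of the fracture. The SAP 13.1.1.11 table works back from the reported fracture date.

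**The concern.** Protocol 10.1.3 and SAP 4.4 list the reporting assessment and the assessments at 1, 2 and 3 months as separate time points. The SAP's selection rules do not keep them separate. A fracture reported 16 or more days after it occurred can yield one questionnaire that meets both definitions. The true first follow-up then moves into the Month 2 slot.

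Two consequences follow for such a woman:

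- **Responder endpoint.** Her Month 1 pain score is compared with itself. The difference is zero, so she is a Month 1 non-responder whatever happened to her pain.
- **Repeated measures models.** Her Month 1 outcome and her at-report covariate are the same number. That row says nothing about recovery after reporting, yet it contributes a perfect outcome-covariate relation to the fit.

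**Working it through.** The plan gives no figure on this point, so there is none to reproduce. The check has four steps.

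**1. Overlap.** At-report window: days 0 to 45. Month 1 window: days 16 to 45. The intersection is days 16 to 45, which is 45 − 16 + 1 = 30 days, the whole Month 1 window. Months 1, 2 and 3 do not overlap one another.

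**2. Does the closest-to-target rule help?** Take visits 30 days apart and a reporting visit on day d after the fracture.

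- d = 10: next visit on day 40. Month 1 is the true first follow-up, with no collision.
- d = 16: follow-ups on days 46, 76 and 106. The reporting visit is the only record in days 16–45, so it becomes Month 1. The first follow-up becomes Month 2, and the third falls after day 105, outside every window.
- d = 31: next visit on day 61, again Month 2.

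For d from 16 to 31 the rule has no second candidate to choose.

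**3. How often?** The documents give no distribution for the lag from fracture to reporting visit. The following are assumptions: day 0 is the fracture date, fracture dates are evenly spread, the questionnaire is completed at the next monthly visit, and the reporting visit may count as a scheduled post-fracture visit.

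Simple count, 30-day spacing:

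- Fracture date counted as day 0: lags 16–30 qualify, 15/31 = 48% (15/30 = 50% without lag 0).
- Fracture date counted as day 1: lags 15–30 qualify, 16/31 = 52% (16/30 = 53% without lag 0).

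Simulation: visits every 30.44 days, 100,000 fractures per scenario, the reporting visit plus three follow-ups up to Month 12, closest-to-target rule. Ranges cover both day counts and fractures spread over 335 or 365 days.

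| Visit jitter | Reporting record selected as Month 1 | No visit in Month 1 window |
|---|---|---|
| none | 48–51% | 2–5% |
| ±3 days | 46–49% | 4–8% |
| ±7 days | 44–47% | 8–11% |

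Sensitivity to the lag, with the fracture date as day 1:

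| Lag evenly spread over | Share colliding |
|---|---|
| 0–10 days | 0% |
| 0–15 days | 1/16 = 6% |
| 0–20 days | 6/21 = 29% |
| 0–30 days | 16/31 = 52% |

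With day 0 at the reporting visit, that visit cannot reach day 16 and the share is 0%. One exception remains under the 45-day rule. If the reporting-visit questionnaire is missing, the next monthly visit, near day 30, becomes the at-report value and is also Month 1. SAP 10.5.4 instead says that missing scores at reporting are multiply imputed, for OPAQ-SV, EQ-5D-5L VAS and BPI.

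**4. Which anchor do the documents use?** Both.

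| Months counted from the fracture | Months counted from reporting |
|---|---|
| Protocol 10.1.3, actual values and changes | Protocol 10.1.3 and SAP 4.4, pain responder |
| SAP 10.5.4, EQ-5D-5L shift tables and LAD | SAP 10.5.4, models for OPAQ-SV, EQ-5D-5L VAS and BPI |
| SAP 13.1.1.11, table label | Protocol 10.5.2.1, summaries by visit since reporting |

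**The case against.** The best reply is that a sensible programmer would never reuse the record. Protocol 7.12 separates the reporting visit from the three monthly visits after it, the endpoint lists treat reporting and Months 1 to 3 as distinct, and much of SAP 10.5.4 counts from reporting. The code that might settle this (SAP 13.4) is redacted. This stands as evidence of intent. It does not change the literal rules in SAP 6.1.1 and 13.1.1.11, which count from the fracture and exclude nothing.

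A reader might infer that about half of reporting visits will double as Month 1. The documents do not support that as a fact. It needs every assumption in step 3, and other readings give 0%. If the fracture date were the confirming image date, which SAP 6.3 uses for time-to-event endpoints, a clinical vertebral fracture x-rayed at or after the reporting visit would not collide. That would spare few cases, because SAP 3.2.2 expects about 85% of clinical fractures to be nonvertebral. Very short lags are also not the obvious case: monthly telephone contacts start only at Month 13 (Protocol Appendix A), so visit spacing largely sets the lag in the double-blind period.

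A reader might also infer bias towards one arm. Visits and windows are the same in both blinded arms, and nothing in the documents points to a direction. Automatic non-response concerns the Month 1 time point. SAP 10.5.4 also analyses improvement within 3 months, where later visits can still show a response.

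Last, the two baseline definitions pick the same record unless a questionnaire falls between the fracture and its reporting. If every fracture is reported at the next visit, none does.

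**Conclusion.** The concern holds as a defect of definition. The Month 1 window is contained in the at-report window, nothing prevents double use of one record, and the anchor is inconsistent. Where double use occurs, the Month 1 pain change is zero and the at-report covariate equals the Month 1 outcome.

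Its frequency cannot be fixed from the documents. It is about 44% to 51% under a fracture-date anchor, evenly spread fractures and completion at the next monthly visit, falling to 0% with lags of 10 days or less or with a reporting-visit anchor and a completed reporting questionnaire.

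Only exploratory post-fracture PRO/ClinRO endpoints are touched, in a subset that SAP 10.5.4 already describes as non-randomised and open to bias. The primary endpoints and the alpha-controlled secondary sequence are unaffected.

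**What to change.** 1. In SAP 6.1.1, define the at-report value as the questionnaire completed at the fracture-reporting visit. If it is missing, treat it as missing and apply the handling in SAP 10.5.4.
2. In SAP 13.1.1.11, count days 16–45, 46–75 and 76–105 from the reporting visit, and state that the at-report record is never used for Months 1 to 3.
3. Align the wording in SAP 10.5.4 that counts from the fracture (EQ-5D-5L shift tables, LAD). Note the change of anchor from Protocol 10.1.3 in SAP Section 11.
4. Use one pre-fracture baseline. SAP 13.1.1.11 (before the fracture date) must be reconciled with SAP 6.1.1 and Protocol 10.5.2.1 (before reporting). Keeping the protocol definition needs no further entry. Adopting the fracture date is a departure, and SAP Section 11 does not list it at present.

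The cost is SAP wording and the matching derivation code. No new data are needed, and the changes should be made before unblinding.
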